in-person. Participants will be asked to sign the electronic consent form on Qualtrics or REDCap, mail a signed paper version back to the research assistant, or drop off a signed paper version to their clinic for research staff to pick up. Alternatively, consenting maybe be done in-person. Participants will also keep a copy of the consent for their records.

Participants randomized to the MORE condition will participate in eight, weekly, two-hour online group sessions led by a clinic or study counselor. Each session will contain 5 to 9 participants and will be conducted online through secure video or phone conferencing. If a participant is unable to join the MORE session through video conference due to technical difficulties at the time of the session, the participant will be instructed to join the session by phone or the participant may go to their clinic and a research or clinic staff member can help them access the intervention through their tablet or a computer. Attendance at each session and reasons for missing sessions will be recorded. Participants randomized to the control condition will continue receiving treatment as usual at their clinic.

All study participants will partake in a total of three interviews lasting up to 120 minutes occurring at baseline, 8-, and 16-weeks (week 1 will be considered the week of the first MORE group session) by video or phone conferencing or in-person. If more than 3 months since baseline survey was administered from start of group (study intervention), clients will be asked to do another baseline survey. Each participant will also have a urine or saliva sample collected during each assessment. This is required to verify self-report of drug use. Due to social desirability, it is common for people to not accurately report drug use; therefore, biochemical verification is the gold standard measure of drug use. Participants will be mailed a urine or saliva test prior to the interview.

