8	Discussion of how to maintain mindfulness practice; finding a sense of meaning and purpose of life; development of mindful recovery plan; imaginal rehearsal of skill learning; mindful breathing							

Treatment as Usual (TAU). In the MMT programs, clients typically come to the clinic regularly (usually 6 days per week at the beginning of treatment) to get their methadone dose; during periods of social distancing or as clients progress through the program and remain abstinent from drugs, they can "take home doses" that they can take on days that they are not required to come to the clinic. Timing of the initiation of take-home doses and the scheduling of clinic days varies across clinics. Clients see their clinic substance abuse counselor for individual

7

Version Number: 15, 2/2/2022 Protocol Number: Pro20190016877 PI Name: [name]

Protocol Title: Mindfulness Oriented Recovery Enhancement (MORE) as an Adjunct to Methadone Treatment RESERVED FOR IRB STAMP
DO NOT MODIFY THIS SPACE

counseling, usually weekly at the beginning of treatment, with decreasing frequency if they remain abstinent and progress through treatment. Depending on clients' stage of MMT and success with remaining abstinent from drugs, they may be required to attend clinic treatment groups. During periods of social distancing, these individual or group sessions may be remote, through video conference or phone. Also, some clients may choose to go to voluntary counseling, educational, or support groups (none of these groups involve coping with pain oriented or are mindfulness-based). All individual treatment characteristics, including methadone dosage, take-home dosing, clinic attendance and attendance at clinic counseling sessions and groups (whether in-person or remotely), will be documented for all study participants and entered as covariates in the analyses.

B. Dependent Variables or Outcome Measures

In addition, the study will explore outcomes among participants in the MORE condition relative to treatment as usual (TAU) in regard to opioid use outcomes such as:

- Time until first opioid lapse (primary outcome)
- Opioid abstinence
- Time until MMT dropout
- Total days of methadone treatment
- Total days of opioid or any drug use
- Trajectories of positive and negative affect
- Drug craving
- Pain severity and pain interference

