4.3 Subject Randomization

Since MORE is a closed group, we will randomize cohorts of 10-18 participants (depending on speed of recruitment) at each site to TAU or MORE with block randomization. Once we recruit at least 10 to 18 participants at a particular clinic, we will randomize participants to MORE or TAU, and the MORE group will begin.

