Hypothesis 1.1. (**Primary Outcome**) MORE will result in longer duration of time to first opioid lapse and MMT dropout than TAU. We will use survival analysis (Kaplan Meier curves and marginal model analysis for multivariate survival data)³⁴ to test effects of MORE vs. TAU on time until first opioid lapse and MMT dropout—evidenced either on EMA, Timeline Follow-Back, urinalysis or medical records (whichever is first). Survival analysis will be run once, at 16 weeks post-baseline. Clustering within cohort will be adjusted in the multivariate marginal model analysis.³⁴ We will estimate the hazard ratios of opioid lapse and MMT dropout when comparing MORE with TAU, controlling for covariates.

Hypotheses 1.2 and 1.3 (Secondary Outcomes). MORE will result in more days of opioid abstinence (or less days of use) and a higher rate of biochemically-verified abstinence over time than TAU. Generalized linear mixed model (GLMM)³⁵ repeated measures analysis will be used. Specifically, identity link will be used for "number of abstinent days" as the dependent variable, and logit link will be used for "opioid abstinence (yes/no via urinalysis)" as the dependent variable. Days of use/abstinence will be assessed via EMA, number of drug use days since last visit and past 30 days, and the Timeline Follow-Back. In cases of conflicting findings across data sources, we will assume the highest number of days of use or lowest number of abstinent days recorded for that period. Analyses will include group (MORE vs. TAU), time, and group by time interactions as the fixed effects independent variables. Correlations among repeated measures and among subjects within cohorts will be modeled using nested random effects. Potential confounders that meet the p<0.10 criterion stated above will be entered as covariates. Linear contrasts will be constructed to test between-group differences in "days of use" or "days of abstinence" separately at each timepoint. In comparing days of use, if a substantial proportion of subjects do not use opioids, resulting in excessive zero days of use, we will use a two-part logistic/linear analysis model.^{36,37}

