Hypotheses 1.4 (**Secondary Outcomes**). MORE will result in more days of MMT and greater decreases in pain severity, pain interference, days of non-opioid drug use, and emotional distress over time than TAU. We will use GLMM to compare days of MMT, pain severity and interference scores, days of non-opioid drug use, and emotional distress among the treatment groups, using the same analytic strategy described above.³⁵

AIM 2 Analyses. Mediational analysis. To test whether the three mediators specified in Aim 2 statistically mediate the effect of treatment on changes in days of opioid use over time, we will conduct a multivariate path analysis via a latent growth curve framework conducted in structural equation modeling software (i.e., MPlus) according to established guidelines³⁸ evaluating 3 regression paths for each mediator: A) 'a' path between treatment indicator and pre-post treatment change in the mediator (e.g., savoring); B) the 'b' path between pre-post treatment change in the mediator (e.g., savoring) and the latent slope (change) of the outcome (e.g., opioid use); and C) the 'c' path between treatment indicator and the latent slope of the outcome (e.g., opioid use). We will emulate similar multivariate analyses from published studies of meditation interventions^{39,40} by testing treatment effects on the latent slope of changes in days of drug use over time as mediated by changes in proposed mechanisms. We will test mediation by evaluating the significance of the joint product of the a and b paths, with bootstrapping used to test the significance of the indirect effect. A similar model will be estimated for changes in pain severity. Path models will be corrected for multiple comparisons. Simultaneous estimation of mediational effects from all three mediators to days of drug use and pain will allow us to determine unique effects of the core therapeutic mechanisms of MORE (mindfulness, reappraisal, savoring) – representing one of the most comprehensive mediation modeling attempts of the MORE intervention research program to date.

Version Number: 15, 2/2/2022 Protocol Number: Pro20190016877 PI Name: [name]

Protocol Title: Mindfulness Oriented Recovery Enhancement (MORE) as an Adjunct to Methadone Treatment RESERVED FOR IRB STAMP
DO NOT MODIFY THIS SPACE

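### The secondary-outcome mixed models do not say whether the cohort effect is common to both arms; if it is, correlation created by the MORE therapy groups is left out of the treatment standard error

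*Combined protocol and SAP*

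**What the plan says.** Section 4.3 builds the trial in cohorts: "we will randomize cohorts of 10-18 participants (depending on speed of recruitment) at each site to TAU or MORE with block randomization". Once a clinic has enough recruits, "we will randomize participants to MORE or TAU, and the MORE group will begin". Randomization is therefore of individuals within a cohort, and every cohort contains both arms. Section 1.3 A gives the MORE group size: "Each session will contain 5 to 9 participants". For the other arm it says "Participants randomized to the control condition will continue receiving treatment as usual at their clinic".

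Under Hypotheses 1.2 and 1.3, section 6.1 A specifies generalized linear mixed models (GLMMs). They use an identity link for abstinent days, a logit link for urinalysis abstinence, and a two-part model if many participants have zero days of use. On fixed effects: "Analyses will include group (MORE vs. TAU), time, and group by time interactions as the fixed effects independent variables". On random effects: "Correlations among repeated measures and among subjects within cohorts will be modeled using nested random effects". Hypothesis 1.4 (days of MMT, pain severity and interference, non-opioid drug use, emotional distress) is analysed "using the same analytic strategy described above".

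The plan gives no arm-specific or MORE-only random term, no ICC and no degrees-of-freedom method. The opening paragraph of the data analysis plan adds, for all analyses, sensitivity analyses of clustering by site, group cohort and therapist.

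**The concern.** The design is partially nested. MORE participants in a cohort share a leader and eight weekly closed sessions, so their outcomes may become correlated through that group. Their TAU counterparts share only recruitment at the same clinic and time.

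The natural reading of the random-effects sentence is visits within subjects within cohorts, with one effect per cohort. Such an effect adds the same amount to both arms, so it drops out of MORE minus TAU. It handles correlation that the arms share, but it cannot represent correlation present in MORE alone. The treatment standard error (SE) is then too small whenever the MORE-group ICC is above zero, and the error favours finding a difference. At stake are the p-values and confidence intervals for the secondary outcomes under Hypotheses 1.2-1.4.

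**Working it through.** The plan states no ICC, SE or error rate for these models, so it has no figure of its own to reproduce on this point.

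**Inputs from the documents.** Total N is 184, allocated 1:1 (sections 1.5 and 4.5). MORE groups have m = 5 to 9 (section 1.3 A) in cohorts of 10-18 (section 4.3). The number of cohorts is K = N/(2m): 184/10 ≈ 18, 184/14 ≈ 13, 184/18 ≈ 10. The nominal level is 5% two-sided; the plan states it for the primary outcome, and it is used here per test, before the Holm adjustment.

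**Assumptions.** The MORE-group ICC is taken over 0 to 0.15. Total variance is 1 in each arm, cohorts are balanced, the outcome is continuous, and there is no dropout.

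**Step 1, true variance of the MORE-TAU difference:** V_true = (1/K)[1/m + (1−ICC)/m + ICC].

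**Step 2, variance reported under a shared cohort intercept:** V_model = 2·MSR/(K·m). MSR pools the within-cell mean square, MSW = 1 − ICC/2, with the cohort-by-arm mean square:

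MSR = [(K−1)(MSW + m·ICC/2) + 2K(m−1)·MSW] / [(K−1) + 2K(m−1)].

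**Step 3, example (m = 7, K = 13, ICC = 0.10):**

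- V_true = (1/13)(0.1429 + 0.1286 + 0.1000) = 0.02857.
- MSW = 0.95, and the cohort-by-arm mean square is 0.95 + 0.35 = 1.30.
- MSR = (12×1.30 + 156×0.95)/168 = 163.8/168 = 0.975.
- V_model = 2×0.975/91 = 0.02143.
- Model SE / true SE = √(0.02143/0.02857) = 0.866.
- Type I error = 2[1 − Φ(1.960×0.866)] = 9.0%.

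**Step 4, all settings.** Each cell gives simulated type I error (40,000 null trials), with the closed-form ratio of model SE to true SE in brackets.

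| m, K | ICC 0.01 | 0.02 | 0.05 | 0.10 | 0.15 |
|---|---|---|---|---|---|
| 5, 18 | 5.2% (0.989) | 5.7% (0.978) | 6.5% (0.948) | 7.6% (0.902) | 9.3% (0.861) |
| 7, 13 | 5.5% (0.984) | 5.9% (0.969) | 6.7% (0.927) | 8.9% (0.866) | 11.0% (0.815) |
| 9, 10 | 5.6% (0.979) | 6.2% (0.960) | 7.5% (0.907) | 10.5% (0.834) | 12.8% (0.775) |

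At ICC 0 the rate is 5.0-5.2%. A second run gave 6.2-7.6% at ICC 0.05 and 7.8-10.3% at 0.10.

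**Step 5, repeated measures.** With three visits and a subject random effect, the week-16 contrast gives 6.2-10.1% over ICC 0.05-0.10. The change-from-baseline (group-by-time) contrast gives 6.4-10.2% at within-subject correlation 0.5. At m = 7 it gives 6.5% and 7.9% (ICC 0.05 and 0.10) at correlation 0.3, and 8.1% and 11.2% at correlation 0.7. Adding a true shared cohort variance of 0.05 changes little: 7.1% and 8.9% at m = 7, single time point.

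**Step 6, other structures, ICC 0.02-0.10.** A separate cohort effect in each arm gives 4.0-4.8%. A MORE-only group term with Satterthwaite degrees of freedom gives 4.9-5.2%.

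**Step 7, attrition.** Section 1.5 needs 47 per group and recruits up to 92. As an illustrative lower bound, scaling groups of 5-9 by 47/92 = 0.51 leaves about 2.6-4.6 analysed. The same closed form then gives 5.6-6.2% at ICC 0.05 and 6.2-7.5% at ICC 0.10.

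**The case against.** The strongest reply is that the plan never says the cohort effect is shared. The random-effects sentence would also fit an effect specific to each cohort-by-arm cell, and that model does not inflate error. This stands: a reader might infer that the plan specifies a wrong model, but the documents support only an under-specification whose natural reading is anti-conservative. That is still a reason to settle the text, because one permitted reading holds the error rate and the other does not.

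Second, no ICC appears in the documents. A rate such as 6-10% might be taken as a property of the trial, but it belongs to assumed ICCs of 0.05-0.10 with full groups. At 0.01-0.02 the excess is about one percentage point or less, and attrition reduces it further. What stands without an assumed value is the direction, for any ICC above zero.

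Third, the planned sensitivity analyses cover group cohort and therapist. They show that clustering was considered, and a therapist term could pick up leader-level correlation, though not differences between groups with the same leader. They leave the main model unchanged and describe no MORE-only term, and a cohort effect entered as a common fixed effect cancels from the contrast in the same way.

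Fourth, a reader might infer that MORE is the only arm in which outcomes can cluster. Section 1.6 A does not support that: of TAU clients it says "they may be required to attend clinic treatment groups", and they also have clinic counselors. Those groups depend on clinic and treatment stage, not on the study cohort, so the narrower statement stands: only MORE has a study-formed group.

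Finally, the Holm adjustment does not answer the point, since it takes each p-value as valid.

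**Conclusion.** The point holds conditionally. If the cohort effect is common to both arms, the secondary models leave MORE-group correlation out of the treatment SE. With complete balanced data and a continuous outcome, per-test type I error is about 5.2-6.2% at ICC 0.01-0.02, 6-8% at 0.05, 8-10% at 0.10 and 9-13% at 0.15. The change contrast can run slightly higher when within-subject correlation is high, and all figures fall if fewer people per group are analysed. If the effect is arm-specific, there is no inflation.

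Two wider readings are not supported. The logit model for urinalysis abstinence and the two-part model share the structure, but they were not simulated, so no error rate is claimed for them. The primary outcome is not affected: it uses a marginal survival model with its own adjustment for clustering within cohort. Nor does the point concern the sample size. It is worth correcting before analysis, as a matter for the secondary outcomes.

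**What to change.** In section 6.1 A, under Hypotheses 1.2-1.3 and by reference under 1.4, state the main model explicitly: a cohort effect (fixed or random), plus a therapy-group random effect that applies to MORE participants only, that is, a MORE coefficient that varies at random by cohort. For the identity-link models, allow arm-specific residual variance and name Satterthwaite or Kenward-Roger degrees of freedom. For the logit or two-part models, use the same MORE-only term and name a suitable small-sample correction. Keep the planned site, cohort and therapist analyses as sensitivity analyses.

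No new data or participants are needed. The cost is a somewhat more complex model and wider intervals. Over ICC 0.05-0.10 the SE rises by roughly 5% (1/0.948 = 1.05) to 20% (1/0.834 = 1.20), and the smaller degrees of freedom widen the intervals somewhat more than that.

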meaningfully related to measures of pain and adjustment to pain, ¹⁴ and have been shown to mediate the therapeutic effects of mindfulness training on chronic pain. ¹⁵

Nonreactivity (Baseline, 8- and 16-- weeks). Nonreactivity to distressing thoughts and emotions will be measured with the Five Facet Mindfulness Questionnaire. This scale is comprised of items such as "When I have distressing thoughts or images, I 'step back' and I am aware of the thought or image without getting taken over by it." These skills appear to tap metacognitive decentering or disengagement from aversive experiences, and have been shown to mediate the effects of mindfulness training on decreased pain. 15

Reappraisal (Baseline, 8- and 16-- weeks). Reappraisal will be measured with the positive reappraisal subscale of the Cognitive Emotion Regulation Questionnaire (CERQ),¹⁷ an internally-consistent subscale (α = .85) which asks the respondent how often they "think I can become a stronger person as a result of what has happened" or "look for positive sides to the matter" to cope with stressful events. Responses are rated on a scale ranging from 1 (almost never) to 5 (almost always). In prior research, scores on this reappraisal scale were prospectively predictive of lower levels of future affective symptoms,¹⁷ and changes in CERQ reappraisal scores mediated the stress-reductive effects of mindfulness.¹⁸ Also reappraisal will be assessed with the 9-item Mindful Reappraisal Of Of Painful Sensations Scale. Responses are rated on a scale ranging from 0 (never do that) to 6 (always do that);

Positive and Negative Affect (Baseline, 8- and 16-- weeks). We will assess positive and negative affect with the valid and reliable Positive and Negative Affect Schedule (PANAS). The PANAS is a 20-item, self-report measure that consists of two scales (positive affect and negative affect) of 10-items each. Participants will rate factors related to positive or negative affect on a scale from 1 (not at all) to 5 (very much).

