PI Name: [name]

Protocol Title: Mindfulness Oriented Recovery Enhancement (MORE) as an Adjunct to Methadone Treatment RESERVED FOR IRB STAMP DO NOT MODIFY THIS SPACE

Savoring (Baseline, 8- and 16-- weeks). Savoring will be measured by the Savoring Beliefs Inventory (SBI), The SBI is a reliable and valid scale that consists of 6 items that assess individuals' perceptions of their ability to derive pleasure through anticipating upcoming positive events, savoring positive moments, and reminiscing about past positive experiences or the Momentary Savoring Scale,²⁷ which assesses the propensity to focus on the moment as a means of intensifying positive experience from naturally rewarding events.

Mindfulness practice. In addition to collecting EMA data we will assess mindfulness practice with the timeline follow-back. The timeline follow-back is a reliable and valid measure where participants are asked to recall and record events within a specified time period on a calendar.

MMT dose, MMT days of treatment, MMT services. This information will be abstracted from participants' clinic charts, with participants' consent.

The following cognitive tasks will be completed on a laptop computer or tablet. The online tasks will be administered through the Inquisit platform. Pre-developed Inquisit scripts exist for each computer task, and participants' encrypted task data will be housed on a secure server "using Secure Sockets Layer (SSL)", the same technology used by online shopping and banking web sites to protect sensitive information transmitted over the web" (https://www.millisecond.com/support/docs/v5/Inquisit.pdf). Each task will be scored within the Inquisit platform according to validated scoring methods.

Inhibitory control, Go-No Go Task (Baseline, 8-weeks): To assess inhibitory control, participants are asked to press the Spacebar on a computer when they see, on the computer screen, a green rectangle (=go) but refrain from pressing the Spacebar when they see a blue rectangle (=no go).²¹ The blue and green rectangles can be vertical or horizontal. The vertical rectangle has a high probability of being green (a go trial) and the horizontal rectangle has a high probability of being blue (a nogo trial). Participants get information about the orientation of the rectangle (=cue) shortly before the color of the rectangle is revealed. Mean reaction times will be derived from the Go/No-Go tasks.

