6.0 Research Data Protection and Reporting

6.1 Data Management and Confidentiality

A. Describe the data analysis plan, including any statistical procedures.

Data Analyses. Analyses will be conducted on an intent-to-treat basis. Adjustment for multiple comparisons using Bonferroni-Holm procedure²⁸ will be applied in outcome analyses. We will first examine baseline between-group differences on demographic and other key variables - those that show a difference of p<.10 will be entered as covariates in the analyses below. Given that this RCT occurs within a naturalistic treatment context (i.e. MMT programs in which study participants will also be receiving usual care), significant group differences in usual treatment (e.g., methadone dose or number of TAU psychotherapy sessions) will be treated as covariates. For all analyses specified below, we will perform sensitivity analyses to test response differences or clustering by site, group cohort, and therapist either as fixed or random effects and assess the robustness of results when accounting for these site and therapist effects. To handle **missing data**, we will conduct a series of sensitivity analyses using pattern-mixture (PM) approaches, ²⁹⁻³¹ assuming missing-at-random (MAR), ³² not-missing-at-random (nMAR) and/or a mix of nMAR and MAR, to assess plausible treatment effects in the presence of missing data. Other PM approaches such as control-based pattern imputation approach or the tipping-point approach will also be considered. ³³ The missing data handling strategy will be carefully selected depending on the distributions, type, and mechanism of missing data (informative vs. non-informative).

Version Number: 15, 2/2/2022 Protocol Number: Pro20190016877 PI Name: [name]

Protocol Title: Mindfulness Oriented Recovery Enhancement (MORE) as an Adjunct to Methadone Treatment RESERVED FOR IRB STAMP
DO NOT MODIFY THIS SPACE

AIM 1 Analyses.

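### The mediation paths use pre-post change in each mediator with no term for its baseline value, which can cost precision on the a path and can create a false b path

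*Combined protocol and SAP*

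**What the plan says.** The model is in section 6.1 A under the Aim 2 analyses (mediation is Aim 3 in section 1.1). It is a multivariate path analysis run "via a latent growth curve framework conducted in structural equation modeling software". Three regression paths are named for each mediator:

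- a: the "path between treatment indicator and pre-post treatment change in the mediator";
- b: the "path between pre-post treatment change in the mediator (e.g., savoring) and the latent slope (change) of the outcome";
- c: treatment to the latent slope of the outcome.

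Mediation is judged on the product of a and b, "with bootstrapping used to test the significance of the indirect effect". The three mediators are estimated together, a similar model is planned for pain severity, and the path models are to be corrected for multiple comparisons.

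The general covariate rule at the start of section 6.1 A compares the arms at baseline, and "those that show a difference of p<.10 will be entered as covariates in the analyses below". Section 1.9 B schedules every mediator at baseline: "Nonreactivity (Baseline, 8- and 16-- weeks"), "Reappraisal (Baseline, 8- and 16-- weeks") and "Savoring (Baseline, 8- and 16-- weeks").

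The text does not say whether change is a difference score, a residualised change or a latent change score. It does not say how the outcome's latent intercept enters. It gives no correlation, effect size or power for mediation.

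**The concern.** A difference score carries the baseline value with a negative sign, so people who start high tend to fall and people who start low tend to rise. This has two possible consequences.

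On the a path, that baseline noise stays in the error term. Randomisation keeps the estimate unbiased, but its variance is larger than it need be.

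The b path is not randomised. If the outcome slope also depends on where the outcome started, and mediator and outcome are correlated at baseline, then mediator change and outcome slope are correlated even when the mediator does nothing to the outcome. This happens within persons, so balance between arms does not remove it and a screen for imbalance does not detect it. It is also separate from the time ordering of mediator and outcome.

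At stake is the claim that MORE works through mindfulness, reappraisal and savoring. The test could miss a real effect on a mechanism, or credit a mechanism that MORE moves but that does not drive opioid use or pain.

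**Working it through.** The plan has no mediation figure to reproduce.

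**Inputs.** From the plan: 92 per group, 184 in total (section 1.5), and 47 per group, 94 in total, the number needed for the primary outcome (sections 1.5 and 6.1 B). Section 6.1 B also gives 85 per group, but only 92 agrees with the total of 184. Assumed: equal mediator SD of 1 at baseline and week 8; baseline to week-8 correlation ρ; baseline mediator-outcome correlation r; outcome autocorrelation k from baseline to week 16; and the effect of MORE on the mediator.

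**a path.**
- Variance of the difference: 1 + 1 − 2ρ = 2(1−ρ).
- Variance after adjusting for baseline: 1 − ρ².
- Ratio: (1−ρ²) / [2(1−ρ)] = (1+ρ)/2, so the efficiency loss is (1−ρ)/2.

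Example at ρ=0.5, 92 per group, assumed effect 0.4 SD. The difference has variance 1, so SE = √(2/92) = 0.147, z = 2.71 and power = Φ(2.71−1.96) = 77%. Adjusted variance is 0.75, so SE = √(0.75×2/92) = 0.128, z = 3.13 and power = 88%. (The noncentral t gives 0.770 and 0.876.)

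| ρ | Efficiency loss | Power at 92 per group, difference vs adjusted | Power at 47 per group, difference vs adjusted |
|---|---|---|---|
| 0.3 | 35% | 63% vs 81% | 37% vs 53% |
| 0.5 | 25% | 77% vs 88% | 49% vs 61% |
| 0.7 | 15% | 94% vs 97% | 71% vs 78% |

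Outside that range the loss is 40% at ρ=0.2, 10% at 0.8 and 5% at 0.9.

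**b path with no true mediator effect.** Within arm, let D = (ρ−1)M0 + error and slope S = (Y16−Y0)/2 = (k−1)Y0/2 + error. Then Cov(D,S) = (1−ρ)(1−k)r/2. Dividing by Var(D) = 2(1−ρ) gives a false coefficient

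b = (1−k)r/4.

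It is zero if r=0 or if the slope does not depend on the starting level (k=1). With an 8-week outcome autocorrelation of 0.5, k = 0.25: r=−0.2 gives −0.0375 and r=−0.4 gives −0.075. Simulation gave about −0.038 and −0.075, returning to about 0 once baseline mediator was added.

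**False indirect effects.** Simulated with a 0.5 SD effect of MORE on the mediator, no mediator effect on the outcome, and an indirect effect declared when a and b are both significant at an uncorrected 5%:

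| N | ρ and k | r=−0.2 | r=−0.3 | r=−0.5 |
|---|---|---|---|---|
| 184 | 0.5 | 9.7% | 15–17% | 35–37% |
| 184 | 0.7 | 6.4% | 8.7% | 17.4% |
| 94 | 0.5 | about 5% | 7.8% | 14.9% |

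With the baseline mediator in both equations, the rates at ρ=k=0.5 and r=−0.3 or −0.5 are about 4–5% at both sample sizes.

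**Check with the planned test.** A percentile bootstrap of a×b (N=184, 400 trials, 300 resamples, ρ=0.5, 8-week outcome autocorrelation 0.7 so k = 0.49) gave 12%, 15% and 36% at r=−0.2, −0.3 and −0.5, and 4–6% with the baseline mediator added. Bootstrapping does not remove the bias.

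**The case against.** Four points on the other side have force.

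- **Parameterisation is open.** A reader might infer that the plan commits to raw difference scores. It does not say so. The model sits in a latent growth framework that follows cited guidelines, and a residualised change would already condition on baseline. A difference is the natural reading, not an established one.
- **The size of the loss is assumed.** A reader might take 15–35% as a property of this trial. It is only (1−ρ)/2 at ρ of 0.7 to 0.3, and the plan gives no ρ. It is a loss of precision, not a bias.
- **False mediation is conditional.** A reader might infer that the b path will be false. That needs a baseline correlation and an outcome slope tied to its starting level; a false indirect effect also needs a non-zero a path. The documents establish none of these. In a simulation with the slope independent of the intercept, the b path rejected in about 5% of trials even at r=−0.4. At r=−0.1 with N=184 (ρ=k=0.5) the false indirect rate was 5.4%. Conditioning on the baseline outcome also removes the bias, and a growth model may do this through its intercept.
- **The simulations are simplified.** They use one mediator and an observed slope, and they omit the planned multiplicity correction. At 0.05/6 = 0.83% (three mediators by two outcomes, an assumed family), the rates at N=184 and autocorrelations of 0.5 fall to 4% at r=−0.3 and 13% at r=−0.5.

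These points limit the claim but do not remove it. The corrected rates still exceed the 0.83% level. Nothing in the text guarantees conditioning on either baseline. The conditions are also plausible: section 1.9 B describes nonreactivity as a mediator of decreased pain and reappraisal as predictive of affective symptoms, and section 4.2 D enrols on a minimum pain level, where regression to the mean is expected.

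**Conclusion.** The point holds in conditional form. The plan names no baseline-mediator term in either path, and its covariate screen does not supply one routinely.

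If change is a simple difference, the a path loses (1−ρ)/2 of its efficiency. At ρ=0.5 and an assumed 0.4 SD effect, that is 77% rather than 88% power with 92 per group. The b path can show a false association. At an uncorrected 5% level, false indirect effects range from about 6% to 37% at N=184, for baseline correlations of −0.2 to −0.5 and autocorrelations of 0.7 to 0.5, and are about 5–15% at N=94. They are lower in absolute terms after the planned correction. All of these figures rest on assumed correlations and effect sizes.

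A reader might extend this to the trial's efficacy results. The documents do not support that: the mediation model is a separate aim, and the primary and secondary treatment comparisons do not use it. The change is worth making because it costs almost nothing.

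**What to change.** In the mediational analysis of section 6.1 A, state how mediator change is parameterised and specify that:

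- each mediator's week-8 value (or its change) is regressed on treatment and on that mediator's own baseline value; the treatment coefficient is the same either way;
- the same baseline mediators are covariates in the equation for the outcome's latent slope, and the outcome's latent intercept is allowed to covary with them;
- this applies to all three mediators and to both opioid use and pain severity, whatever the p<.10 screen shows.

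The cost is a sentence or two of analysis text, three covariates per model and a few degrees of freedom. No new data are needed. The change does not address other confounding of the b path or the time ordering of mediator and outcome.
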